#### Hematoma expansion – a surrogate marker for unfavourable outcome

Outcome after intracerebral hemorrhage is closely related to whether brain bleeding expands after onset, so called hematoma expansion (HE), and is associated with a poor outcome. Especially, in the presence of oral anticoagulation hematoma volume is usually large and HE occurs frequently. Observational studies report rates of HE ranging from 36% in patients with primary ICH (e.g. without prior treatment with anticoagulants) to 45-56% in patients on vitamin K-antagonists (VKA). In patients with ICH not-associated with anticoagulation, extravasation of contrast medium within the hematoma – the spot-sign – is a radiological biomarker to identify patients with a higher rate of HE of up to 61%. There are no reports on the significance of the spot-sign in NOAC-ICH. HE is used as primary outcome measure in trials for ICH in spot-sign positive patients and treatment with tranexamic acid (NCT01702636, which excluded patients with NOACS) or recombinant factor VIIa (NCT00810888) and as a secondary outcome measure in other trials in ICH.

#### Tranexamic acid

Tranexamic acid (TA) is an anti-fibrinolytic drug that can be administered intravenously or orally and is used in a number of bleeding conditions to reduce bleeding. In a recent trial (CRASH-2) in 20,000 patients with major bleeding following trauma, TA significantly reduced mortality with no increase in vascular occlusive events. Treatment was most effective when given rapidly; delayed administration was associated with lack of efficacy and potential harm. In a subgroup analysis of patients with traumatic intracerebral hemorrhage, TA showed a non-significant trend to reduced mortality and death of dependency. However, patients in CRASH-2 were younger and had less co-morbidities than those with spontaneous intracerebral hemorrhage. A single-center randomized pilot-trial showed feasibility of rapid administration of TA in patients with intracerebral hemorrhage. Since 2012, an investigator-initiated phase III trial (TICH-II) investigates whether TA is safe and reduces death and dependency after hyperacute (within 8 hours of onset) primary ICH (i.e. no prior treatment with anticoagulants). Patients with NOAC-ICH are excluded from this trial. In an animal model of traumatic systemic NOAC-bleeding, TA was given in addition to treatment with the specific antibody idarucizumab or PCC and was beneficial in both treatment regimes. We therefore hypothesize that TA might be a beneficial treatment in NOAC-ICH.

## **3.2 Investigational Product**

### 3.2.1 Description and Manufacture

Intravenous tranexamic acid (Cyklokapron, 100mg/ml 5ml ampoules, Pfizer Manufacturing Authorisation: PL 00057/0952) or matched placebo of intravenous Sodium Chloride 0.9% 5ml ampoules (Hameln, Manufacturing Authorisation: 1502 / 0006R). Tranexamic acid 100mg/ml 5ml ampoules are a licensed product and the summary of the product characteristics is available for investigator.

### 3.2.2 Blinding and unblinding procedure

The tailoring and randomisation of the study medication will be performed by the Hospital Pharmacy of the USB according to GMP. Each study medication package consists of either experimental or comparator using licensed and labelled products packed in an outer box which is blinded. The packed and therefore blinded study medication will be provided to the study team after randomization. An unblinded study nurse will prepare the study medication and administer it to the patient. The used vials are packed again in the outer box and sealed. In case of unblinding, the box with the used vials can be opened and assignment is visible.

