### 3.2.4 Packaging, Labelling and Supply (re-supply)

The investigator shall take responsibility for and shall take all steps to maintain appropriate records and ensure appropriate supply, storage, handling, distribution and usage of the study medication in accordance with the protocol and any applicable laws and regulations.

Product descriptions

Product name	Potency	Dosage Form
Tranexamic acid (Cyklokapron)	1000 mg / 10 ml	Solution for infusion
NaCl 0,9% Mini-Plasco Fresenius	0,9%	Solution for infusion

Study medication will be packed in an outer box and labelled in accordance with regulatory requirements. Labels for the infusion bags will also be packed in the outer box.

Receipt and dispensing of study medication must be recorded at the study site. Study medication must

not be used for any purpose other than that stated in the protocol.

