## **6. STUDY DESIGN**

### **6.1 General study design and justification of design**

This trial is a randomized, controlled, double-blinded, placebo-controlled phase IIb/III trial investigating whether tranexamic acid is beneficial for the treatment of NOAC-ICH. Up to now, no evidence proven treatment for NOAC-ICH exists. The trial will be performed in 7 Swiss Stroke Centers recruiting 109 patients. Extension to international centers is intended.

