#### **8.1.4 Storage Conditions, dispense and return**

The packs will be stored at room temperature and protected from excessive heat and freezing in a restricted access area. Stability data exists which demonstrates that Tranexamic Acid is stable at temperatures between -20°C and 50°C. Temperature monitoring will not be required. The IMP will be clearly labelled for clinical trial use only. Each pack will be a numbered box containing either tranexamic acid or placebo according to a computer-defined sequence.

The local site investigator is responsible for ensuring trial treatment accountability, including reconciliation of trial treatment and maintenance of trial treatment records, throughout the course of the study in accordance with local regulatory requirements. Responsibility can be delegated to the site pharmacy clinical trials staff.

Following randomisation the participant will be allocated a treatment pack number. Specifically authorised personnel will retrieve the appropriate pack number and complete the participant name, date of randomisation and participant number. Pack number allocation will be checked and countersigned by the research staff and the nursing staff administering the treatment. The treatment will be prescribed on the participant's treatment chart as trial medication. The nurse administering the study treatment is unblinded, which represents a potential bias. Nevertheless, all personal will receive order not to communicate to anybody the treatment and whether it contains tranexamic acid or placebo. Nursing staff administering the treatment is not involved in the evaluation of any outcome parameters.

Dispensing will be recorded on the appropriate trial specific accountability forms. Trial treatment must not be used for any other purpose than the present study. Returned trial treatment that has been dispensed to a participant must not be re-dispensed to a different participant. Any unused drug will be returned to pharmacy.

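### The same unblinded nurse prepares and gives the study drug, so blinding of bedside observation, first notice of adverse events and co-intervention is not assured

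*Combined protocol and SAP*

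**What the plan says.** Section 3.2.2 describes kits of commercial, labelled vials inside a masked outer box, handed over once the patient is randomised. It then says: "An unblinded study nurse will prepare the study medication and administer it to the patient". After preparation, "The used vials are packed again in the outer box and sealed". Section 3.2.4 adds: "Labels for the infusion bags will also be packed in the outer box". Table 1 in section 3.2.3 gives a 10-minute loading infusion followed by an 8-hour infusion, in saline in both arms.

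Section 8.1.4 confirms the nurse's status and is open about it: "The nurse administering the study treatment is unblinded, which represents a potential bias". It sets two safeguards: "Nevertheless, all personal will receive order not to communicate to anybody the treatment and whether it contains tranexamic acid or placebo", and "Nursing staff administering the treatment is not involved in the evaluation of any outcome parameters". On handling of the kit it says: "Pack number allocation will be checked and countersigned by the research staff and the nursing staff administering the treatment". Section 6.1 describes the design as follows: "This trial is a randomized, controlled, double-blinded, placebo-controlled phase IIb/III trial".

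**The concern.** Two tasks with different blinding needs are given to one person. Whoever opens the box sees the product name. Whoever hangs a diluted, labelled bag need not. Joining the tasks puts someone who knows the arm in contact with the patient while the drug is running, and the protocol gives no reason for it.

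Blinded CT reading protects the measurement of the haematoma. It does not protect what happens to the patient before the 24-hour scan, or what is noticed and passed on. All adverse events are collected in hospital up to day 7 (section 10), and an investigator can record only what comes to notice. Among the secondary outcomes in section 5.2, neurosurgical intervention depends on clinical decisions. Symptomatic expansion can be met through a change in GCS, for which the schedule in section 9.1 has no row. Extra vigilance or co-treatment in one arm could blur a real difference or produce a spurious one, most plausibly in the safety data.

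**Working it through.** The plan gives no figure on this point, so the check sets its statements side by side.

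**1. Where the arm becomes visible.** The vials are labelled commercial products and the outer box is masked (3.2.2). The vials go back into the sealed box after use (3.2.2), both arms are diluted in saline (Table 1), section 8.1 calls the regimens identical, and bag labels are supplied (3.2.4). It follows that opening the box is apparently the only revealing step. This is an inference: no section says that the finished bags look alike or that the labels hide the arm.

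**2. What is protected.**

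| Activity | What the documents say | Protection |
|---|---|---|
| CT volumes | Raters blinded (6.2, 9.2.1) | Stated blinding |
| Evaluation of listed outcomes | Administering nurses excluded (8.1.4) | Stated bar |
| CRF completion | Local investigators (12.1.1) | Not described as unblinded |
| SAE assessment | Chief Investigator with treating practitioners (9.2.4); Sponsor-Investigator (10.1.1) | Not described as unblinded |
| Antidote use entered at randomisation | A minimisation factor, so recorded before allocation (6.2.1) | Order of events |
| First notice of adverse events during infusion | Observer not stated | None stated |
| Co-treatment or escalation after the infusion starts | Local SOPs (3.3); any treating clinician may stop study medication (7.4) | Only the order not to disclose |

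The last two rows are the gap. An order not to tell others does not govern the nurse's own conduct, and a bar on evaluating outcomes does not cover noticing or reporting an event that someone else later evaluates.

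**3. Whether a blinded person could run the infusion.** This needs indistinguishable bags. Section 3.2.4 lists the drug at 1000 mg per 10 ml, so the active maintenance dose of 1000 mg is 10 ml in 250 ml. For placebo, Table 1 also puts 10 ml in 250 ml, whereas section 8.1.2 gives 250 ml of saline with no 10 ml addition. If the 10 ml is added to a full bag, the active bag holds 250 + 10 = 260 ml. The placebo bag holds 260 ml under Table 1 and 250 ml under section 8.1.2, a difference of 10/250 = 4%. Whether this would be noticed is unknown, but the two sections do not agree.

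**4. Whether a size can be given.** A conditional calculation is possible. With a pooled two-proportion z-test, two-sided 0.05, n = 109/2 = 54.5 per arm and no missing data:

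power = Φ{ [ |p1 − p2|·√n − 1.96·√(2·p̄·(1 − p̄)) ] / √( p1(1 − p1) + p2(1 − p2) ) }

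For 54% vs 27%: (0.27 × 7.382 − 1.96 × 0.694) / 0.667 = 0.948, so power is 82.8%. Lowering the placebo rate by an assumed 2, 4 or 6 points gives 76.9%, 69.9% or 62.2%. These shifts have no source in the documents. The figures show what any bias of that size would do to power, not that this procedure causes one.

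**The case against.** The strongest reply is that this is a disclosed choice with safeguards. The protocol names the bias, orders silence and keeps administering nurses out of outcome evaluation. Symptomatic expansion, thromboembolic events, neurosurgical intervention and death are all listed outcomes, so their evaluation falls under that bar. Volumes are segmented semi-automatically by a blinded core lab. Antidote use recorded for minimisation precedes allocation and cannot be driven by knowledge of the arm. All of this stands, and it narrows the concern to co-intervention and first notice of events.

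A reader might go further and infer that bedside care and event reporting are unblinded. The documents do not support that. They show one unblinded role. The people who complete CRFs and assess serious events are not described as unblinded. No section makes the administering nurse the patient's carer for the 8 hours: section 3.2.2 speaks of a study nurse, section 8.2 of a research nurse and section 8.1.4 of nursing staff. Nor does any section exclude that role, which is why the supportable wording is that blinding is not assured.

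A reader might also take the power figures in step 4 as the expected damage. They assume that one nurse's knowledge moves the expansion rate of a whole arm, and the documents identify no haemostatic decision that this nurse controls.

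On feasibility, countersigning a pack number does not prove that a second person is free to prepare the drug and then stay out of that patient's care. This too stands, and it is why a fallback is needed.

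**Conclusion.** The point holds in limited form. Sections 3.2.2 and 8.1.4 unblind the person who gives the infusion, without a stated need. The safeguards leave bedside observation, first notice of adverse events and co-intervention uncovered in a trial described as double-blinded. The likely effect on the blinded CT outcome is small. The effect on adverse-event ascertainment and on decisions such as neurosurgical intervention is more plausible, but the documents do not allow either to be quantified. The conclusion assumes that a made-up bag with a suitable label does not reveal the arm, which is reasonable but not stated. Changing this would be a cheap improvement to a choice that the protocol itself discloses.

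**What to change.** - **Separate the tasks in 3.2.2 and 8.1.4.** The unblinded nurse prepares both bags away from the bedside, applies labels that do not reveal the arm and reseals the vials. That nurse then takes no further part in the patient's care, event observation or reporting. A blinded ward nurse runs the infusions. Amend the statement that the administering nurse is unblinded to match.
- **Provide a fallback.** Where a site cannot separate the roles for a patient, extend the bar in 8.1.4 to observing or reporting adverse events and to influencing co-treatment. Flag the patient on the CRF for a sensitivity analysis.
- **Reconcile the placebo maintenance bag.** Table 1 (section 3.2.3) and section 8.1.2 must agree on whether 10 ml is added, and the protocol should state that bags and labels are indistinguishable between arms.

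The cost is protocol wording, site instruction and one CRF item. Bag labels are already supplied, and research and nursing staff already handle each pack together. The downside is a handover and a preparer who is not the bedside nurse, which may be harder out of hours. The fallback covers that case without extra staff.

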### 3.2.3 Trial treatments

The treatments to be used in this trial are outlined below in Table 1:

Drug	Dose	Administration	Route of Administration	Use
Tranexamic acid (Cyklokapron)	2000 mg	Loading dose of 1000 mg in 100 ml normal saline over 10 minutes followed by 1000 mg in 250 ml normal saline as a continuous infusion over 8 hours	Intravenous	Experimental
Normal Saline	0,9 %	Loading dose of 10 ml in 100 ml normal saline over 10 minutes followed by 10 ml in 250 ml normal saline as a continuous infusion over 8 hours	Intravenous	Comparator

Table 1: Trial treatments

### 3.2.4 Packaging, Labelling and Supply (re-supply)

The investigator shall take responsibility for and shall take all steps to maintain appropriate records and ensure appropriate supply, storage, handling, distribution and usage of the study medication in accordance with the protocol and any applicable laws and regulations.

Product descriptions

Product name	Potency	Dosage Form
Tranexamic acid (Cyklokapron)	1000 mg / 10 ml	Solution for infusion
NaCl 0,9% Mini-Plasco Fresenius	0,9%	Solution for infusion

Study medication will be packed in an outer box and labelled in accordance with regulatory requirements. Labels for the infusion bags will also be packed in the outer box.

Receipt and dispensing of study medication must be recorded at the study site. Study medication must

not be used for any purpose other than that stated in the protocol.

### **3.2.5 Storage Conditions**

Study medication must be stored in a secure, limited-access location under the storage conditions specified on the label

### **3.2.6 Known Side Effects**

Gastrointestinal disorders (nausea, vomiting, diarrhoea) may occur but disappear when the dosage is reduced. Hypotension has occasionally been reported after rapid intravenous infusion. Rare instances of colour vision disturbances have been reported following long-term use. Rare cases of thromboembolic events have been reported. Rare cases of allergic skin reactions have also been reported (see Appendix A). Tranexamic acid will counteract the thrombolytic effect of fibrinolytic preparations but these would be contra-indicated in patients with haemorrhagic stroke.

## **3.3 Explanation for choice of comparator (or placebo)**

The comparator of the IMP is placebo in addition to best medical treatment in a Stroke Center according to local SOPs following national and international guidelines. The trial steering committee encourages all investigators to evaluate the use of idaruzicumab for patients suffering ICH under dabigatran or andexanet alpha for patients suffering ICH under treatment with a factor Xa-inhibitor (edoxaban, rivaroxaban or edoxaban) if available. This approach guaranties that NOAC-ICH-patients participating on TICH-NOAC will have the chance to benefit from a potentially beneficial agent on top of state-of-the-art treatment, available for all participants.

## **3.4 Risks / Benefits**

### Benefit

Patients participating in TICH-NOAC may directly benefit from a potentially beneficial treatment (tranexamic acid) in addition to standard medical state-of-the-art treatment. This benefit can consist in a reduced rate of hematoma expansion and an improved clinical outcome.

### Risks:

Patients may experience an increased risk for thromboembolic complications including ischemic stroke or deep venous thrombosis due to treatment with tranexamic acid although this risk was not elevated compared to placebo in prior trials involving tranexamic acid.

### Trial Procedures

Patients suffering intracerebral haemorrhage under a prior treatment with a NOAC will be included in this study shortly after admission to a participating center and after informed consent has been obtained (see page 17). After inclusion, patients will receive two intravenous infusions containing either tranexamic acid or placebo (a bolus containing of 100ml over 10 minutes followed by a 8 hours infusions of 250ml). 24 hours after admission, a single run non-contrast CT head scan will be performed (day 2). Patients will be followed up in-hospital until day 7/discharge with a final outpatient follow-up at 90 days. If patients are unable to come for the follow-up visit to the study center, a telephone interview with the patient or care giver will be performed.

### Details of radiation materials and dose

The doses from CT scans will vary between sites with different models of equipment and between different sizes of patient.

A CT of the brain will give an average of 1.5mSv but this could be up to a maximum of 5mSv. So a typical dose from CT due to research exposures would be 1.5mSv, but could be as high as 5mSv.

A 1.5mSv dose would be roughly equivalent to 8 months of exposure to natural background radiation to a member of the public resident in Switzerland. A 5mSv dose is roughly equivalent to 2¼ years of background received by a member of the public resident in Switzerland.

A follow-up CT-scan is often performed also in clinical routine, in order to search for either (i) HE or (i) complications such as intraventricular expansion or hydrocephalus which is important for management

and prognosis. Thus participation in TICH-NOAC must not necessary mean an exposition to additional radiation. Contrast agents are not involved in the study CT-scan at follow-up.

Risk Assessment (induction of fatal cancer)

Based on a risk coefficient for developing fatal radiation induced cancer (all ages) of 5%/Sv (ICRP), this would lead to a risk of radiation exposure incurred as part of the trial similar to the annual risk of dying from an accident in the home. This is classed as an intermediate risk and the required benefit should be aimed directly at diagnosis, cure or prevention of disease.

## **4. STUDY OBJECTIVES**

### **4.1 Overall Objective**

To demonstrate that treatment with TA for NOAC-ICH is beneficial. The results of this trial will determine whether TA should be used for the treatment of NOAC-ICH.

### **4.2 Primary Objective**

The primary objective is to show that treatment with TA in patients with NOAC-ICH reduces the rate of HE as a surrogate marker for unfavourable outcome.

### **4.3 Secondary Objectives**

Secondary objectives of this trial are to show that treatment with TA for NOAC-ICH increases the proportion of patients having a favourable clinical outcome and to show that TA influences hematoma expansion in different definitions.

## **5. STUDY OUTCOMES**

### **5.1 Primary Outcome**

The primary outcome measure is hematoma expansion (HE). In line with prior research, HE is defined as an increase of 33% relative or 6ml absolute growth between ICH-volume on baseline CT and on follow-up-CT at 24 ± 3 hours.

### **5.2 Secondary Outcomes**

Secondary outcome measures are

- (I) modified Rankin Scale (mRS) 0–4 at three-months;
- (II) mRS 0–3 at three-months;
- (III) Categorical shift in mRS at three-months;
- (IV) Absolute ICH growth volume by 24 ± 3 hours, adjusted for baseline ICH volume;
- (V) Symptomatic HE defined as HE and neurological deterioration of NIHSS >4 points or GCS >2 points
- (VI) Death due to any cause by three-months;
- (VII) major thromboembolic events (myocardial infarction, ischemic stroke, pulmonary embolism – safety endpoints)
- (VIII) NCH intervention (including craniectomy, EVD, hematoma evacuation)
- (IX) In-hospital mortality

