	
 
7. major thromboembolic events (myocardial infarction, ischemic stroke, pulmonary embolism)
 
8. NCH intervention (including craniectomy, EVD, hematoma evacuation)
 
9. In-hospital mortality
 

Statistical Hypothesis	TA reduces rate of HE in patients with NOAC-ICH compared to placebo in addition to best medical treatment
Inclusion Criteria	
 
- Acute intracerebral hemorrhage (symptom onset <12h)
 
- Prior treatment with a novel direct oral anticoagulant (apixaban, dabigatran, edoxaban or rivaroxaban; last intake <48hours OR proven NOAC activity by relevant coagulation assays)
 
- Age >18 years, No upper age limit
 
- Informed consent has been received in accordance to local ethics committee requirements
 

Exclusion Criteria	
 
- Severe pre-morbid disability (modified Rankin scale >4)
 
- Anticoagulation with VKA
 
- Secondary intracerebral hemorrhage (e.g., AVM, tumor, trauma) Note it is not necessary for investigators to exclude underlying structural abnormality prior to enrolment, but where an underlying structural abnormality is already known, these patients should not be recruited.
 
- Glasgow coma scale <5
 
- pregnancy
 
- Planned neurosurgical hematoma evacuation within 24 hours (before follow-up imaging)
 
- Pulmonary embolism/deep vein thrombosis within the last 2 weeks.
 

Sample Size	109
Study Centers	Basel (coordinating center), Bern, Luzern, Zürich, Aarau, St. Gallen, Hirslanden
Randomization	1 : 1
Intervention	intravenous tranexamic acid (1g loading dose given as 100 ml infusion over 10 minutes, followed by another 1g in 250 ml infused over 8 hours) or as comparator placebo (normal saline 0.9%) administered by identical regimen.
Study Procedure	The study contains of 5 study visits (Screening-/Randomization visit, Follow-up-visit on day 2, day 7, discharge from primary care hospital and 90 days) and lasts 3 months. Clinical measures (mRS, NIHSS) and adverse events will be obtained at every visit after randomization. On day 2, a follow-up native head CT-scan for determination of hematoma expansion will be performed.

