#### Exclusion criteria:

- Severe pre-morbid disability (modified Rankin scale >4)
- Anticoagulation with VKA
- Secondary intracerebral hemorrhage (e.g., AVM, tumor) Note it is not necessary for investigators to exclude underlying structural abnormality prior to enrolment, but where an underlying structural abnormality is already known, these patients should not be recruited.
- Glasgow coma scale <5
- pregnancy
- Planned neurosurgical hematoma evacuation within 24 hours (before follow-up imaging)
- Recent pulmonary embolism/deep vein thrombosis within the last 2 weeks

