As the IMP is administered once and has a short half-life, serious adverse events occurring within the first 7 days will be assessed for seriousness, expectedness and causality. In addition fatal SAEs and safety outcome events (VTE, recurrent stroke, TIA, MI, PAD and seizures) will be reported until day 90.

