## 10. SAFETY

During hospitalisation in the participating center until day 7, all adverse events (AE) and all serious adverse events (SAEs) are collected, fully investigated and documented in source documents and case report forms (CRF). After discharge from the participating hospital and/or day 7 (what occurs first), only study outcome events (death, ischemic vascular events) are collected as SAE until end of study. Study duration encompassed the time from when the participant signs the informed consent until the last protocol-specific procedure has been completed.

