### 11.3 Statistical criteria of termination of trial

The DSMC will recommend to the TSC that the trial be stopped if there is proof beyond reasonable doubt (with a 99% CI) of overall benefit with the active treatment or if there is a lower level of evidence suggesting overall hazard. Evidence of hazard will include effect on the primary outcome (HE) and analysis of safety endpoints, as specified in the protocol (death, VTE, ischaemic events, seizures, serious adverse events).

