### 11.4 Planned Analyses

Analysis will be by intention-to-treat; Missing outcome data will be imputed assuming worst possible outcome.

The primary outcome (HE) is to be compared between treatment and control arms adjusted for baseline volume using binary logistic regression. Although both baseline covariate adjusted and unadjusted results will be reported, baseline covariate adjusted analysis is prespecified as the primary outcome analysis for this trial.

As secondary outcome analyses, the proportions of mRS 0–4, mRS 0–3, and mortality outcomes will be compared between active and placebo arms of the trial adjusted for baseline volume using a binary logistic regression model. Analysis of the categorical shift in mRS will also be undertaken on the full range of the mRS using the Cochran–Mantel–Haenszel shift test and proportional odds logistic regression, subject to the validity of shift analysis model assumptions. Other secondary outcome analyses will be carried out according to standard statistical principles for comparison of parametric or nonparametric distributions as appropriate.

Exploratory analysis will be run on the primary and secondary outcomes, with adjustments for baseline

variables such as age, Glasgow coma scale (GCS), presence of IVH, and ICH location, and in the following subgroups: onset-to-treatment time (<six vs. >six-hours), baseline ICH volume (<30 vs. >30 ml), anatomical location (deep, lobar, or cerebellar), IVH (absent vs. present), GCS (>12 vs. 8–12), and age (<70 vs. >70), presence of spot-sign. These analyses will be hypothesis generating, as the trial is not powered for them.

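### Outcome VII counts pulmonary embolism but not deep vein thrombosis, and no listed outcome counts seizures, although other sections treat VTE and seizures as safety outcomes

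*Combined protocol and SAP*

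**What the plan says.** The listed endpoint appears three times with the same content. The synopsis has "major thromboembolic events (myocardial infarction, ischemic stroke, pulmonary embolism", section 5.2 has "VII) major thromboembolic events (myocardial infarction, ischemic stroke, pulmonary embolism – safety endpoints", and section 9.2.3 repeats the three components and has them collected at each visit.

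Other sections draw the boundary differently:

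- Section 3.4 (Risks) says that patients may face an "increased risk for thromboembolic complications including ischemic stroke or deep venous thrombosis due to treatment with tranexamic acid". It adds that earlier trials of the drug showed no elevation over placebo.
- Section 9.2.3.1, last paragraph: "safety outcome events (VTE, recurrent stroke, TIA, MI, PAD and seizures) will be reported until day 90".
- Section 10, on the period after day 7 or discharge: "only study outcome events (death, ischemic vascular events) are collected as SAE until end of study".
- Section 11.3 has evidence of hazard include "analysis of safety endpoints, as specified in the protocol (death, VTE, ischaemic events, seizures, serious adverse events".
- Section 7.1 treats the two forms of venous thromboembolism together as an exclusion: "Recent pulmonary embolism/deep vein thrombosis within the last 2 weeks".

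On analysis, section 11.4 names methods for the mRS outcomes and mortality. For the rest it says only: "Other secondary outcome analyses will be carried out according to standard statistical principles".

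**The concern.** The point is what the safety endpoint counts and whether the plan counts it the same way everywhere. Section 3.4 names two thromboembolic harms of the drug, ischaemic stroke and DVT. Outcome VII counts the first and leaves out the second. A patient with a symptomatic DVT and no embolism after study drug is not an event in the listed thromboembolic outcome. A patient with a seizure is not an event in any of the nine listed secondary outcomes.

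This matters because of who is enrolled. Participants were taking a NOAC, and section 3.1 gives stroke prevention in atrial fibrillation and treatment of venous thrombosis among the approved uses. They receive an antifibrinolytic, and section 3.3 encourages sites to consider a specific reversal agent as well. Section 3.4 draws its reassurance from the large trauma trial, whose patients, according to section 3.1, were younger and had fewer co-morbidities than patients with spontaneous intracerebral haemorrhage. Section 4.1 says that this trial will determine whether the drug should be used. Its own thromboembolic comparison should therefore cover the harms that the protocol names.

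**Working it through.** There is no plan figure to reproduce. The check sets the lists side by side. The documents expand neither VTE nor PAD, so I take VTE in its usual sense of PE plus DVT and leave PAD as written.

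| Place | MI | Ischaemic stroke | PE | DVT | PAD | TIA | Seizures |
|---|---|---|---|---|---|---|---|
| Synopsis item 7, 5.2 (VII), 9.2.3 | yes | yes | yes | no | no | no | no |
| 3.4 Risks | not named | yes | not named | yes | not named | not named | not named |
| 9.2.3.1, to day 90 | yes | as recurrent stroke | within VTE | within VTE | yes | yes | yes |
| 10, after day 7 or discharge | as ischaemic vascular event | as ischaemic vascular event | not named | not named | not named | not named | not named |
| 11.3, evidence of hazard | as ischaemic event | as ischaemic event | within VTE | within VTE | not named | not named | yes |

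Four things follow.

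1. **Outcome VII reads as a closed list.** The next item, VIII, introduces its examples with the word *including*; VII has no such word in any of its three places.
2. **Capture and endpoint differ.** Under 9.2.3.1, DVT (as VTE) and seizures are reported to day 90. Neither is in a listed outcome. The general sentence in 11.4 covers secondary outcomes, so it does not reach them, and 11.4 plans no other safety analysis.
3. **Capture is not secure.** Section 10 restricts collection after day 7 or discharge to death and ischaemic vascular events. It names neither VTE nor seizures, which conflicts with 9.2.3.1.
4. **What outcome VII can show.** Write A for all patients with MI, ischaemic stroke, PE or DVT, and D for those whose only such event is DVT. The outcome VII count is A − D. The difference between arms in outcome VII is therefore the difference in A minus the difference in D. If the whole excess lies in D, the two terms are equal and the outcome VII difference is zero, whatever the sample size.

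**The case against.** The strongest reply has three parts.

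**The events are captured.** Section 9.2.3.1 is part of 9.2.3, the section on safety outcomes, and calls VTE and seizures safety outcome events. The reference in 11.3 to endpoints specified in the protocol can point there. This stands against any reading that DVT and seizures go unrecorded or that 11.3 has no source. It does not supply a listed outcome or a final comparison by arm, and section 10 puts collection after day 7 in doubt.

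**The narrow list is a choice.** The endpoint is called *major*, and MI, ischaemic stroke and PE form a coherent severe subset. That is a legitimate design, though the documents do not state this reason. It would justify keeping the composite. It would not justify leaving VTE and seizures outside every listed outcome when 9.2.3.1 and 11.3 treat them as safety outcomes or endpoints.

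**A detailed SAP is still to come.** Section 11 says that one will be drawn up before the code is broken, and safety tables could be set there. This is true, and it makes the change easy. It does not remove the conflict between the protocol's own lists.

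A reader might also infer stronger claims that the documents do not support:

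- *That the safety conclusion is biased.* The list applies equally to both arms. Outcome VII understates an excess only if the excess lies in the omitted events.
- *That the protocol expects DVT from the drug.* Section 3.4 calls it a possibility and adds that earlier trials saw no elevation. The drug-risk text in 3.2.6 and 3.4 does not name seizures; their case rests on 9.2.3.1 and 11.3.
- *That the board and the final report will use different endpoints.* The lists make this possible; no section says that it will happen.
- *That a third or more of events would be missed.* Any share rests on assumed rates. With 5% of patients having a listed event and a further 2–4% only an omitted one, the share left out is 2/7 to 4/9, or 29–44%. With a 10% base it is 2/12 to 4/14, or 17–29%. Nothing in the documents favours either base.

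**Conclusion.** The concern holds as a gap in endpoint definition and planned analysis, together with an inconsistency between safety lists. Outcome VII omits DVT, a harm that section 3.4 names as possible. Neither DVT nor seizures is in a listed outcome or an analysis planned in 11.4, although 9.2.3.1 has both reported to day 90 and 11.3 has the board weigh both. Section 10 conflicts with 9.2.3.1 on collection after day 7 or discharge.

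The one firm statement of size is structural: an excess confined to DVT would not appear in outcome VII. The documents give no event rates, so no share of missed events and no amount of bias can be stated. The reading assumes that VTE includes DVT and that the list in outcome VII is closed. The primary outcome and its analysis are unaffected. The change is worth making because it is cheap and closes a gap in the listed thromboembolic comparison.

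**What to change.** Use one safety-event list in the synopsis, 5.2, 9.2.3, 9.2.3.1, 10 and 11.3.

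- Choose one of two forms for the thromboembolic outcome. Either widen outcome VII to MI, ischaemic stroke, VTE (PE or symptomatic DVT) and peripheral arterial events, or keep the present *major* composite and add VTE including symptomatic DVT as its own safety outcome.
- Add seizures as a separate safety outcome.
- State whether TIA counts, and define VTE and PAD.
- In 11.4 or the detailed SAP, report all of these by arm to day 90, as a composite and by component.
- Reconcile section 10 with 9.2.3.1 so that these events are collected to day 90.

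The cost is wording. The study schedule already records adverse events at the day 90 visit and 9.2.3.1 already has these events reported to then, so no new visit or test is needed. If the change counts as substantial, section 2.10 requires ethics committee and authority approval before it takes effect. The wider composite would mix events of different severity. Reporting by component handles this, and the second form leaves the existing composite unchanged.
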